6.4 Primary Independent Variable (Exposure)

The study population will be classified into 3 groups based on exposure: 1) Ethicon Manual Circular Staplers; 2) Medtronic EEA™ Circular Stapler with DST Series™ Technology; and 3) Medtronic EEA™ Circular Stapler with Tri-Staple™ Technology.

- [Redacted]
- [Redacted]
- [Redacted]

6.5 Dependent Variables (Outcomes)

Anastomotic leak within 30 days post-index procedure. AL will include all new AL cases identified during the index admission and those identified during a new admission within 30 days post-index procedure. A 30-day follow-up period is chosen as AL occurs at a median of 12 days (range, 3-30 days) after a colorectal procedure¹⁴ and it is the standard post-operation follow-up study period for most studies assessing AL after stapled anastomosis.

As there is no specific diagnosis code for AL in the International Classification of Diseases, 10th Revision, Clinical Modification (ICD-10-CM) taxonomy, the cumulative incidence of AL can only be estimated via either surrogate diagnoses or procedures which usually occur concomitantly with a leak, e. g., an abscess, peritonitis, a fistula or a post-index surgery stoma formation — a surgical treatment for severe AL.

As such, the presence of an ICD-10-CM diagnosis code for anastomotic leak surrogate diagnoses, such as fistula of intestine, peritonitis, or peritoneal abscess during the index admission or re-admission within 30 days post-index procedure, or the presence of an ICD-10-Procedure Coding System (ICD-10-PCS) procedure code indicating a diverting stoma occurred within 1-30 days post-index procedure will be used to define AL in the PHD. A similar approach was used in other studies assessing the risk of AL using electronic health records (EHR), such as PHD¹⁷ or Nationwide Inpatient Sample database¹⁸. The list of diagnosis codes is summarized in [Table A- 2](#), and the list of ICD-10-PCS codes indicating diverting stoma is summarized in [Table A- 3](#).

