5.2.1 Primary Objectives

- 1) To estimate the cumulative incidence and 95% confidence intervals (CI) of AL within 30 days post-index procedure stratified by study device, and by patient characteristics (including demographic, clinical, procedural, hospital, and provider characteristics).
- 2) To estimate the unadjusted and adjusted relative risk and 95% CIs of AL within 30 days post-index procedure for Ethicon Manual Circular Staplers compared to Medtronic EEA™ Circular Stapler with Tri-Staple™ Technology.
- 3) To estimate the unadjusted and adjusted relative risk and 95% CIs of AL within 30 days post-index procedure for Medtronic EEA™ Circular Stapler with DST Series™ Technology compared to Medtronic EEA™ Circular Stapler with Tri-Staple™ Technology.

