This study will include two head-to-head comparisons: Ethicon Manual Circular Stapler versus Medtronic EEA™ Circular Stapler with Tri-Staple™ Technology; and Medtronic EEA™ Circular Stapler with DST™ Technology versus Medtronic EEA™ Circular Stapler with Tri-Staple™ Technology. The index procedure will be defined as the initial procedure in which the device of interest was used. The index admission will include the time from admission to discharge. Propensity score weighting (PSW) will be used for confounding adjustment, followed by log-binomial regression for risk estimation.

Stoma creations during colorectal resection are reportedly to reduce the incidence of AL or the AL-related complications¹⁴⁻¹⁶, secondary analyses will be conducted separately in those with and without a diverting stoma procedure prior to or on the same day as the index procedure (i.e., left-sided colorectal surgery) during the index admission.

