6.3 Sample Selection

Inclusion Criteria

Patients who meet all of the following criteria will be included in this study:

- 1) Billing charges for a study device (Ethicon Manual Circular Stapler, Medtronic EEA™ Circular Stapler with DST Series™ Technology, or Medtronic EEA™ Circular Stapler with Tri-Staple™ Technology) between January 1, 2019, and June 30, 2022 (or latest available data)
- 2) Undergoing a left-sided colorectal surgery (i.e., the index procedure), defined as presence of a qualifying procedure code for left-sided colorectal surgery (see [Table A-1](#))
- 3) Aged 18 years or older at the index procedure.

Exclusion Criteria

Patients who meet any of the following criteria will be excluded:

- 1) Patient encounters where more than one study device (Ethicon Manual Circular Stapler, Medtronic EEA™ Circular Stapler with DST Series™ Technology, or Medtronic EEA™ Circular Stapler with Tri-Staple™ Technology) was used in the same index procedure
- 2) Missing patient age or sex
- 3) Presence of an admission diagnosis indicating anastomotic leak (See ICD-10-CM in the [Table A-2](#)) during the index admission noted as present on admission*

*Present on admission will be identified with “Yes” in the present on admission field in the PHD.

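### The diagnosis limb of the leak outcome is not confined to the 30 days after surgery within the index stay, so surrogate diagnoses that escape the present-on-admission exclusion can be counted at the wrong time

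*Supplement*

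**What the plan says.** - Section 5.2.1 sets the target as the cumulative incidence "of AL within 30 days post-index procedure stratified by study device".
- Section 6.5 opens with the same window, "Anastomotic leak within 30 days post-index procedure", and continues: "AL will include all new AL cases identified during the index admission and those identified during a new admission within 30 days post-index procedure".
- The operative sentence in 6.5 has two limbs. The diagnosis limb accepts fistula, "peritonitis, or peritoneal abscess during the index admission or re-admission within 30 days post-index procedure". The stoma limb uses a "procedure code indicating a diverting stoma occurred within 1-30 days post-index procedure will be used to define AL in the PHD".
- Section 6.2: "The index admission will include the time from admission to discharge".
- Section 6.3, exclusion 3, removes patients with a Table A-2 diagnosis "during the index admission noted as present on admission". Its footnote adds: "Present on admission will be identified with “Yes” in the present on admission field in the PHD".
- Section 6.6.2 and Table A-5 keep urgent and emergent admissions, diverticulitis and obstruction in the cohort.
- Section 6.9.1.2 again speaks of new cases within 30 days. Neither section says how a diagnosis is judged to be new.

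**The concern.** An analyst who codes the operative sentence literally will search the whole index stay for a Table A-2 code. The plan already recognises that events can precede surgery within that stay: it treats a stoma formed before or on the day of the operation as a baseline covariate and keeps it out of the outcome. Diagnoses get no such separation.

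Take a patient admitted with obstruction who develops an abscess in hospital on day 3 and is operated on day 4. The code is not present on admission, so exclusion 3 does not apply, and the working rule counts a leak from an anastomosis that did not yet exist.

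What is at stake is the primary relative risk. Events that no stapler could have caused add the same amount to numerator and comparator, which dilutes a real difference. In a safety comparison that is the unwelcome direction. Section 8 says that outcome misclassification should be non-differential, but does not discuss this dilution. The only analysis in 6.9.4 addresses loss to follow-up, not event timing.

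**Working it through.** **1. Which diagnoses the written rule counts**

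| Timing of the Table A-2 diagnosis | Exclusion 3 | Operative sentence in 6.5 | Stated outcome |
|---|---|---|---|
| Present on admission, POA Yes | Patient removed | Not reached | Not an event |
| Arises in hospital before surgery, POA No | Stays | Counted | Not an event |
| POA blank or undetermined | Stays | Counted | Unknown |
| After surgery, up to day 30 | Stays | Counted | Event |
| After day 30, still in the index stay | Stays | Counted | Not an event |

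The operative sentence and the stated outcome conflict in the second and fifth rows. The third row is unresolved. The stoma limb has no such rows, because of its 1-30 day window.

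**2. Can the word 'new' close the gap?** Only if a diagnosis can be placed before or after the procedure. Section 6.1 describes a date-stamped log of billed items, but diagnoses recorded for each hospitalization. No rule dates a diagnosis relative to surgery.

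**3. The plan's own power figures.** Inputs from Section 6.8 and Table 2: 6,000 target and 500 comparator patients, one-sided 0.025, comparator risk 2% or 3%. With pooled variance,

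power = Φ[(p₂ − p₁ − 1.96·s₀)/s₁],

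where s₀ is the pooled and s₁ the unpooled standard error of the difference.

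- Risk 3%, relative risk 2: pooled risk (500×0.03 + 6,000×0.06)/6,500 = 0.0577; s₀ = 0.01085; s₁ = 0.00822; (0.03 − 0.02127)/0.00822 = 1.06; power 0.856, as in Table 2.
- Risk 2%, relative risk 2: s₀ = 0.00895; s₁ = 0.00675; power 0.642, as in Table 2.

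The other four rows of Table 2 reproduce as well. Table 2 is not wrong as a calculation.

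**4. Illustration of dilution.** The documents give no rate of mistimed codes. Assume that 15-30% of patients are urgent or emergent and that 1-3% of those carry such a code. The false-event rate f is then 0.15×0.01 = 0.15% to 0.30×0.03 = 0.9%, taken as equal in both arms. With comparator risk b and true relative risk 2,

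observed relative risk = (2b + f)/(b + f).

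| b | f | Observed relative risk | Power |
|---|---|---|---|
| 2% | 0 | 2.00 | 0.642 |
| 2% | 0.15% | 4.15/2.15 = 1.93 | 0.62 |
| 2% | 0.5% | 4.5/2.5 = 1.80 | 0.57 |
| 2% | 0.9% | 4.9/2.9 = 1.69 | 0.53 |
| 3% | 0 | 2.00 | 0.856 |
| 3% | 0.15% | 6.15/3.15 = 1.95 | 0.84 |
| 3% | 0.5% | 6.5/3.5 = 1.86 | 0.81 |
| 3% | 0.9% | 6.9/3.9 = 1.77 | 0.78 |

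The low end is small. Only the top of both guesses combined gives a material loss.

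**The case against.** The strongest reply is that the plan already handles the obvious case. Exclusion 3 removes patients admitted with peritonitis, abscess or fistula flagged present on admission. That stands. A reader might infer from the operative sentence that pre-operative peritonitis or abscess in general is scored as a leak; the documents do not support this. The exposure is what exclusion 3 leaves behind.

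Second, the governing definition says new cases within 30 days, and nothing instructs the analyst to count later events. That stands too. The day-30 part is a conflict between the stated window and the working rule, not an instruction to count late events.

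Third, if diagnoses carry no day stamp, the POA field is the natural timing tool, and using it is reasonable. This explains the asymmetry with the stoma limb but does not remove it. POA separates disease at admission from disease acquired in hospital; it does not separate before from after surgery.

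Fourth, a reader might infer that the false events bias the comparison differentially, because they cluster in urgent cases. The documents weaken that. Admission type and primary diagnosis are in the propensity model (6.9.2), poorly balanced variables are added to the outcome model, and Table B-6 would show incidence by admission type and primary diagnosis for each device. The dilution argument is untouched, since balancing case mix does not remove false events common to both arms.

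**Conclusion.** The gap is real and lies in the primary outcome, but it is confined to three groups: hospital-onset diagnoses before surgery, codes with a POA value that is neither Yes nor No, and diagnoses after day 30 of a long index stay. Followed literally, Section 6.5 counts all three, against its own stated outcome.

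Non-differential events of this kind move the relative risk toward 1. The size cannot be derived from the documents. The figures of 1.93-1.69 (2% comparator risk) and 1.95-1.77 (3%) for a true value of 2.0 rest wholly on the assumed 0.15-0.9% per arm and on equal rates in both arms. The point should be settled before analysis because the repair is cheap and the planned power at 2% risk and a relative risk of 2 is only 0.642 to begin with. It does not invalidate the design.

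**What to change.** 1. **Section 6.5.** Reconcile the diagnosis limb with the 30-day outcome. Restrict index-stay codes to post-procedure days 0-30 where they can be dated. Where they cannot be dated, say so and name it as a limitation.
2. **Section 6.9.4, early-surgery analysis.** Repeat the primary comparison in patients operated on the day of admission or the next day (or in elective admissions). There, a code not present on admission can hardly precede surgery. The plan already relies on procedure timing to classify stomas.
3. **Section 6.9.4, unclear POA values.** Where a Table A-2 code has a POA value other than Yes or No, run the analysis with these codes counted as events and again with them not counted.

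Two simpler remedies fall short. Counting only POA No codes still counts hospital-onset disease before surgery. Dropping every patient whose outcome code has an unclear POA value could delete true leaks, and could bias the device comparison if POA completeness varies by hospital.

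The cost is a change of wording and one or two extra analyses on data already held. The early-surgery subset will be smaller and its estimate less precise, which matters with about 500 comparator patients, so it should be read as a check on direction and size, not as a second test.

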6.6 Other Variables

6.6.1 Patient Demographics/Clinical Characteristics

- Age: mean and category in years at index procedure (18-44; 45-64; 65-74; ≥75)
- Sex (Female or Male)
- Race (White, Black, Other, unknown)
- Comorbidity Index (Charlson Comorbidity Index: 0; 1-2; 3-4; ≥5).

The Charlson Comorbidity Index (CCI) is a sum of weighted scores for 19 conditions. It represents the comorbidity burden and is commonly used for adjustment of comorbidities in observational studies.¹⁹

- Comorbid conditions: (Diagnosis code list for comorbid conditions is provided in [Table A- 4](#)).
 - Alcohol dependency
 - Cardiovascular diseases (CVD): CVD will be categorized based on ICD-10-CM diagnoses for cerebrovascular disease, congestive heart failure, ischemic heart disease, myocardial infarction, or peripheral artery disease.
 - Chronic obstructive pulmonary disease
 - Coagulation defects
 - Diabetes
 - Hypertension
 - Immunosuppression/Immunodeficiency
 - Kidney disease
 - Malnutrition
 - Obesity

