6.9 Data Analysis

6.9.1 Primary Descriptive analysis

6.9.1.1 Demographic, clinical, and procedural characteristics

Descriptive analyses will be first performed for demographic, clinical, and procedural characteristics of patients at the time of the index procedure where a study device was used. Descriptive statistics will be calculated for all study cohorts, including pre- and post- weighted patients by study device. Categorical variables will be summarized by frequencies and proportions and continuous variables will be summarized by means and standard deviations or medians and interquartile ranges. Balance is evaluated using absolute standardized differences (ASD). Nominal variables with more than two categories are summarized using a generalization of the absolute standardized difference for binary covariates. See the expected outputs in [Table B- 1](#), [Table B- 2](#), [Table B- 3](#), [Table B- 4](#), and [Table B- 5](#))

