6.9.2 Primary Comparative analysis

The goals of comparative analyses are to: 1) estimate the RR of AL for Ethicon Manual Circular Staplers compared to Medtronic EEA™ Circular Stapler with Tri-Staple™ Technology; 2) estimate the RR of AL for the Medtronic EEA™ Circular Stapler with DST Series™ Technology compared to Medtronic EEA™ Circular Stapler with Tri-Staple™.

The primary analyses will be conducted separately for the comparison between Ethicon Manual Circular Stapler versus Medtronic EEA™ Circular Stapler with Tri-Staple™ Technology and the comparison between Medtronic EEA™ Circular Stapler with DST™ Technology and Medtronic EEA™ Circular Stapler with Tri-Staple™ Technology. See the expected outputs in [Table B- 7](#) and [Table B- 8](#).

A propensity score weighting (PSW) method will be used to control for potential confounders by balancing the distribution of baseline demographic, clinical, and procedural characteristics between the comparison groups. The following baseline variables will be considered in the propensity score model based on their clinical relevance to the safety of the device: patient demographics (age, sex, and race), clinical characteristics (CCI, comorbid conditions, diverting stoma occurred prior to or on the same day as the index procedure), procedural characteristics (procedure year, surgical site, primary diagnosis, surgical approach, and admission type), and hospital and provider

RWE23-SAF-001:Comparative safety study to assess the risk of AL of 2-row vs 3-row circular staplers

characteristics (hospital region, hospital location, hospital setting, hospital bed size, and surgeon specialty).

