6.9.4 Sensitivity analysis

PHD is not a longitudinal patient database; rather, it is a longitudinal hospital database for the duration of continuous participation for each institution. The treatment pathway for each patient is not fully observed. Patients who receive care at another hospital after the index procedure, even within PHD, will be represented as a new patient. To minimize the potential impact of misclassification of study outcome resulting from the loss of follow-up, a sensitivity analysis will be conducted by repeating the primary analysis among patients from hospitals

RWE23-SAF-001:Comparative safety study to assess the risk of AL of 2-row vs 3-row circular staplers

with at least 30 days continuous enrollment in PHD after the patients' index procedure. See the expected outputs in [Table B- 7](#), [Table B- 8](#), [Table C- 9](#), [Table C- 10](#), [Table C- 11](#), and [Table C- 12](#).

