Coagulation defects	D65, D66, D67, D68.0, D68.1, D68.2, D68.3%, D68.4, D68.5%, D68.6%, D68.9	Coagulation defects
Diabetes	E11.%, E10.%, E13.%, O24.%, E08.%, Z79.4, Z79.84	Diabetes mellitus, Gestational diabetes, Secondary diabetes, long term (current) use of insulin/oral antidiabetic drugs
Hypertension	I10, I11%, I12%, I13%, I15%	Hypertension
Immunodeficiency/immunosuppression	D80%, D81%, D82%, D83%, D84%	immunodeficiencies
	Z92.25	Personal history of immunosuppression therapy
	Z79.52	Long term (current) use of systemic steroids
	B20	AIDS/HIV
Kidney disease	N18%, N19, I12.0, I13.1%, N03.2, N03.3, N03.4, N03.5, N03.6, N03.7, N05.2, N05.3, N05.4, N05.5, N05.6, N05.7, N25.0, Z49.0%, Z94.0, Z99.2	Renal diseases
Malnutrition	E41, E42, E43, E44%, E46, E63%	Malnutrition, nutritional deficiencies
Obesity	E66.0%, E66.1, E66.2, E66.8, E66.9, Z68.3%, Z68.4%	Obesity, body mass index (BMI) 30-39, BMI 40 or greater

'%' at the end of the code denotes any value for subsequent characters.

RWE23-SAF-001:Comparative safety study to assess the risk of AL of 2-row vs 3-row circular staplers

Table A- 5: Diagnosis Codes (ICD-10-CM) for Indications of Surgery

PRIMARY DIAGNOSIS	CODE	CODE DESCRIPTION
Malignant neoplasms	C18.6	Malignant neoplasm of descending colon
	C18.7	Malignant neoplasm of sigmoid colon
	C18.8	Malignant neoplasm of overlapping sites of colon
	C18.9	Malignant neoplasm of colon, unspecified
	C19	Malignant neoplasm of rectosigmoid junction
	C20	Malignant neoplasm of rectum
Benign neoplasm	D12.4	Benign neoplasm of descending colon
	D12.5	Benign neoplasm of sigmoid colon
	D12.6	Benign neoplasm of colon, unspecified
	D12.7	Benign neoplasm of rectosigmoid junction
	D12.8	Benign neoplasm of rectum
Diverticular disease or Diverticulitis	K57.2%	Diverticulitis of large intestine
	K57.3%	Diverticular disease of large intestine
	K57.8%	Diverticulitis of intestine, part unspecified
	K57.9%	Diverticular disease of intestine, part unspecified
Intestinal obstruction	K56.2	Volvulus
	K56.6%	Other and unspecified intestinal obstruction

'%' at the end of the code denotes any value for subsequent characters.

Table A- 6: Diagnosis Codes (ICD-10-CM) for Conversion of Minimally Invasive Procedure to Open Procedure

CODE	CODE DESCRIPTION
Z53.31	Laparoscopic surgical procedure converted to open procedure
Z53.32	Thoracoscopic surgical procedure converted to open procedure
Z53.33	Arthroscopic surgical procedure converted to open procedure

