APPENDIX B: MOCK-UP TABLES—Primary Analysis

Table B- 1: Study cohort attrition

Criteria	Ethicon Manual Circular Staplers		Medtronic EEA™ Circular Stapler with DST™ Technology		Medtronic EEA™ Circular Stapler with Tri-Staple™ Technology	
	N	% Retained	N	% Retained	N	% Retained
Include all patients having billing charges for either study device of interest between January 1, 2019 and June 30, 2022						
Include patients with a left-sided colorectal surgery, during the same episode of admission as the billing charge for device of interest						
Include patients aged 18 years or older at the index procedure						
Exclude patients with use of both a target device and comparator device in the index procedure						
Exclude patients with missing age or sex						
Exclude patients with an admission diagnosis indicating anastomotic leak during the same episode of admission as the billing charge for device of interest						
Number of patients with a diverting stoma prior to or at the same day as the index procedure during the index admission						
Number of patients without a diverting stoma prior to or at the same day as the index procedure during the index admission						

RWE23-SAF-001:Comparative safety study to assess the risk of AL of 2-row vs 3-row circular staplers

Table B- 2: Patient Characteristics at the Index Admission before Propensity Score Weighting: Ethicon Manual Circular Staplers vs. Medtronic EEA™ Circular Stapler with Tri-Staple™ Technology

	Ethicon Manual Circular Staplers		Medtronic EEA™ Circular Stapler with Tri-Staple™ Technology		Absolute Standardized Difference
	n	%	n	%	
N					
Sex: Male					
Age					
Mean (Standard Deviation)					
18-<45 years					
45-<65 years					
65-<75 years					
75 years or older					
Race					
White					
Black					
Other					
Unknown					
Procedure year					
2019					
2020					
2021					
2022, Q1-Q2					
Surgical site					
Rectum					
Sigmoid					
Descending colon					
Others					
Surgical approach					
Open					
Laparoscopic					
Robotic assisted					
Unknown					
Primary diagnosis					
Malignant neoplasms					
Benign neoplasm					
Diverticular disease or Diverticulitis					
Intestinal obstruction					
Others					
Diverting stoma occurred prior to or on the same day as the index procedure					
Cardiovascular Diseases - Overall					
Cerebrovascular Disease					
Congestive Heart Failure					
Ischemic Heart Disease					
Myocardial Infarction					

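### No rule ensures that the comorbidities and Charlson index in the propensity score predate surgery, so acute codes caused by a leak could be adjusted for, pulling the RR toward 1

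*Supplement*

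**What the plan says.** Section 6.6.1 lists ten comorbid conditions and the CCI. For the conditions it says "Diagnosis code list for comorbid conditions is provided in" Table A-4. For the CCI it gives score categories and a reference, with no code list. Neither has a look-back window or a POA condition.

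Table A-4 mixes chronic conditions with codes that can arise after an operation. The coagulation row begins "D65, D66, D67, D68.0, D68.1, D68.2". The cardiovascular rows include I21/I22 (myocardial infarction), I60 to I63 (within cerebrovascular disease) and I50% (heart failure). The malnutrition row includes E43, E44% and E46.

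Section 6.9.2 introduces its covariate list with "The following baseline variables will be considered in the propensity score model". The list includes the CCI and the comorbid conditions, and the section later describes every variable in the model as a prespecified confounder.

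Three passages bear on timing:
- Section 6.9.1.1 describes "characteristics of patients at the time of the index procedure where a study device was used".
- The characteristics tables (B-2 to B-5, C-1 to C-8) carry titles such as "Patient Characteristics at the Index Admission before Propensity Score Weighting: Ethicon Manual Circular Staplers".
- Section 6.2 states "The index admission will include the time from admission to discharge".

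The POA field appears once, in the footnote to Section 6.3 ("in the present on admission field in the PHD"), where it serves only to exclude leak diagnoses already present. Section 6.5 counts new leaks found during the index admission as outcomes.

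**The concern.** A propensity score should contain only what was fixed before the device was used. If a comorbidity is read from all diagnosis codes of the index stay, an infarction, coagulopathy or malnutrition code that followed a leak enters the model as if it were a patient trait.

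The direction is predictable. If the target device leaks more, its patients acquire more of these codes. The plan weights the comparator group to resemble the target group, so comparator patients carrying such codes are weighted up, and these are disproportionately patients who leaked. The weighted comparator risk rises and the RR moves toward 1. Section 4 asks whether 2-row staplers carry a higher leak risk, so the bias would partly hide the effect the study is looking for.

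**Working it through.** **Textual check**

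| Item | Rule that places it before surgery? |
|---|---|
| Diverting stoma covariate (6.6.2) | Yes: on or before the procedure day |
| Leak diagnoses for exclusion (6.3) | Yes: POA = Yes |
| Comorbid conditions (6.6.1, Table A-4) | None |
| CCI (6.6.1) | None, and no code list |

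The index admission runs to discharge (6.2) and leaks in that stay are outcomes (6.5). Coded over the whole stay, the covariate and outcome windows overlap.

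**Inputs for the illustration**

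The plan gives no figure for this bias. Comparator risk 3% and RR 2 (so 6%) are a row of Table 2. That row reproduces with a pooled-variance test of two proportions, 6,000 against 500, one-sided 0.025:
- pooled risk = (360 + 15)/6,500 = 0.0577
- null SE = √[0.0577 × 0.9423 × (1/6,000 + 1/500)] = 0.01085
- alternative SE = √[0.06 × 0.94/6,000 + 0.03 × 0.97/500] = 0.00822
- power = Φ[(0.03 − 1.96 × 0.01085)/0.00822] = Φ(1.06) = 0.856, as stated

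The point does not rest on Table 2. Background prevalences, added probabilities after a leak, and the share of leaks in the index stay are all assumptions, because the documents give none.

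**Formula**

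Let b be the background probability of a code and a the probability that a leak adds it.
- P(code | index-stay leak) = 1 − (1 − b)(1 − a)
- Weighted comparator risk = Σ over code patterns of P(pattern | target) × P(leak | pattern, comparator)
- Weighted RR = 0.06 / weighted comparator risk

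**One code, b = 0.10, a = 0.33, all leaks in the index stay**
- P(code | leak) = 1 − 0.90 × 0.67 = 0.397
- Code prevalence, target: 0.06 × 0.397 + 0.94 × 0.10 = 0.1178
- Code prevalence, comparator: 0.03 × 0.397 + 0.97 × 0.10 = 0.1089
- Comparator leak risk with the code: 0.03 × 0.397/0.1089 = 0.1094
- Comparator leak risk without it: 0.03 × 0.603/0.8911 = 0.0203
- Weighted comparator risk: 0.1178 × 0.1094 + 0.8822 × 0.0203 = 0.0308
- Weighted RR = 0.06/0.0308 = 1.95

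If half of leaks fall in the index stay, P(code | leak) = (0.397 + 0.10)/2 = 0.2485 and the same steps give 1.99. With a true RR of 1 the two prevalences are equal and the result is exactly 1.

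**Five independent codes, b = 0.10 each, a equally spaced over the range shown**

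| Range of a | All leaks in index stay | Half in index stay |
|---|---|---|
| 0.10–0.15 | 1.95 | 1.99 |
| 0.15–0.30 | 1.83 | 1.95 |
| 0.25–0.40 | 1.66 | 1.87 |

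The background prevalence matters greatly. With all leaks in the index stay and a = 0.25–0.40, b = 0.02 gives 1.35 and b = 0.20 gives 1.83. With a = 0.10–0.15, b = 0.20 gives 1.98.

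**Would the plan's checks show it?**

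In the one-code example the absolute standardized difference before weighting is (0.1178 − 0.1089)/√{[0.1178 × 0.8822 + 0.1089 × 0.8911]/2} = 0.028. Across other one-code scenarios (RR 1.5 to 2.5, comparator risk 2% or 3%) the largest was 0.078. All are below the 0.10 threshold in Section 6.9.2. Keeping the balancing analyst away from outcome data does not help, because the outcome information sits inside the covariates. The only sensitivity analysis (6.9.4) concerns hospital enrollment.

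**The case against.** Several points on the other side stand.

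- **The source is inferred.** Section 6.6.1 does not say that codes come from the whole index stay. The plan calls the variables baseline and describes patients at the time of the procedure. Although Section 6.9.4 warns that "PHD is not a longitudinal patient database", Section 8 says records within one institution are linked, so earlier encounters at the same hospital could be used. A reader might infer that the plan prescribes post-operative coding. It does not; it states a pre-procedure intent and leaves out the rule that would enforce it.
- **Not every comorbidity is affected.** A reader might extend the point to all of Table A-4. COPD (including an exacerbation code), hypertension, obesity and diabetes mark chronic disease whenever they are coded. Infarction, stroke and heart failure are components of one cardiovascular variable; if that variable enters as a single term, a post-leak infarction in a patient with known cardiovascular disease changes nothing.
- **Timing dilutes the effect.** Section 6.5 cites a median leak time of 12 days and counts leaks found at readmission. Complications of those leaks are coded in the readmission.
- **Precision is low.** With 500 comparators at 3% and 6,000 target patients at 6%, the unweighted SE of log RR is √(0.97/15 + 0.94/360) = 0.259, giving a 95% CI of about 1.20 to 3.33 around RR 2. A shift to 1.95 is well inside that.

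These points limit scope and size. They do not supply the missing rule: a stated intent cannot separate codes within a stay, and a programmer following the plan could take every matching code.

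**Conclusion.** The plan has a real specification gap. Nothing in Sections 6.6.1 or 6.9.2 or Table A-4 ensures that the acute-capable codes (I21/I22, I60 to I63, I50%, D65/D68.x, E43/E44/E46) and the matching CCI components predate surgery, although the plan sets timing for the stoma covariate and uses the POA field for leak exclusion. If these codes are taken from the whole index stay, the bias is toward 1 when a true difference exists, and in this model it cannot create a difference where there is none.

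The size cannot be known from the documents and is probably small to moderate: near 1.95 to 1.99 for one code against a true RR of 2, and larger if several rare codes often follow index-stay leaks. The lower five-code figures are scenarios that assume independent codes, weighting on every code pattern, no other confounding and chosen complication rates. A reader might take them as an estimate of the study's bias; the documents do not support that. This is a should-fix point.

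**What to change.** In Section 6.6.1 and Table A-4:
- Count the acute-capable codes listed above, and the matching CCI components, only if POA is Yes in the index stay or the code was recorded at an earlier encounter at the same hospital.
- Count clearly chronic conditions and history or status Z codes regardless of the flag, so that genuine confounders are not lost.
- Give the CCI code list and apply the same rule to it.
- Use these versions in the propensity model and in all characteristics tables (B-2 to B-6, C-1 to C-8).

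In Section 6.9.4, add a sensitivity analysis that leaves the acute-capable codes out of the propensity model. It also covers outpatient index encounters and records with a missing flag.

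The cost is a short text change, a filter on a field the study already uses, and one further run. The downside is a slight loss of sensitivity for these conditions where the flag is missing. No sample size or power figure changes. The rule should be set before the weights are built.
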